8.1.5 Eczema Activity and Severity Index (EASI)

[REDACTED]

corticosteroids, topical PDE4 inhibitor (e.g., crisaborole), and/or calcineurin inhibitors or is using

[REDACTED]

8.1.6 SCORing Atopic Dermatitis (SCORAD)

[figure not shown]
The SCORAD will be measured at the visits specified in the SoA. The SCORAD grading system

[REDACTED]

8.1.7 Pruritus Numerical Rating Score

The intensity of pruritus will be recorded daily by the subject in an e-Diary using the pruritus NRS. At the visits specified in the SoA, the pruritus NRS will be completed by the subject at the study center using the e-Diary and should be assessed at about the same time each day. The pruritus NRS will ask subjects “On a scale of 0 to 10, with 0 being “no itch” and 10 being “worst itch imaginable”, how would you rate your itch at the worst moment during the previous 24 hours?”. [Yosipovitch 2019] The daily (24-hour) pruritus NRS will be recorded and the weekly mean of the daily pruritus NRS will be calculated. The pruritus NRS is presented in Figure 2. Subjects should begin recording daily pruritus NRS scores starting at Day 1.

Figure 2 Pruritus Numeric Rating Scale

8.1.8 Patient-Oriented Eczema Measure (POEM)

[REDACTED]

8.1.9 Dermatology Life Quality Index Questionnaire (DLQI)

[REDACTED]

8.1.10 Skin Pain Numerical Rating Scale

The skin pain numerical rating scale was developed for AD subjects by Newton, et. al. [Newton 2019]. Subjects will be asked about the “worst skin pain” over the prior 24-hour period and respond on an 11-point scale between 0 = ‘no pain’ to 10 = ‘worst imaginable pain’.

8.1.11 Patient Global Assessment (PtGA)

[REDACTED]

8.1.12 Asthma Control Questionnaire (ACQ)

[REDACTED]

8.1.13

[REDACTED]

[REDACTED]

8.1.14 Atopic Dermatitis Sleep Scale

The three-item ADSS captures the self-reported impact of itch on sleep disturbance each day, including: difficulty falling asleep (Item 1); number of night-time awakenings (Item 2), and difficulty falling back asleep after waking (Item 3) during the previous night [[Silverberg 2021](#)]. Each ADSS item is scored individually. For Items 1 and 3, subjects will be asked to select a score ranging from 0 (“not at all”) to 4 (“very difficult”). For Item 2, subjects select the number of times they woke up each night, ranging from 0 to 29 times. Subjects are only to answer Item 3 if their answer to Item 2 is greater than 0.

8.2 Safety Assessments

Planned time points for all safety assessments are provided in the SoA.

8.2.1 Physical Examinations

- A complete physical examination will include, at a minimum, assessments of the [Cardiovascular, Respiratory, Gastrointestinal, and Neurological] systems. Height and weight will also be measured and recorded. At screening only, skin tone should be assessed using the [Fitzpatrick](#) skin type scale (I to VI).
- A brief physical examination will include, at a minimum, assessments of the (skin, lungs, cardiovascular system, and abdomen [liver and spleen]).
- Investigators should pay special attention to clinical signs related to previous serious illnesses.

8.2.2 Vital Signs

- Vital signs will consist of body temperature, pulse rate, blood pressure, and respiratory rate.
- Blood pressure and pulse measurements will be assessed with a completely automated device. Manual techniques will be used only if an automated device is not available.
- Blood pressure and pulse measurements should be preceded by at least 5 minutes of rest for the subject in a quiet setting without distractions (e.g., television, cell phones) and with the subject in a seated or supine position.
- Vital signs (to be taken before blood collection for laboratory tests) will consist of 1 pulse and 1 blood pressure measurement with the subject in a seated or supine position.

8.2.3 Electrocardiograms

- Triplicate 12-lead ECG will be obtained as outlined in the SoA (see [Section 1.3](#)) using an ECG machine that automatically calculates the heart rate and measures PR, QRS, QT, and QTc intervals. Refer to [Section 7.0](#) for QTc withdrawal criteria and any additional QTc readings that may be necessary.
- Triplicate 12-lead ECGs will be recorded with a maximum interval of 5 minutes between the first and the third ECG. The ECGs will be recorded after at least 10 minutes of rest in the

supine position using an automated device equipped with computer-based interval measurements (with no/minimal disturbance by procedures).

8.2.4 Clinical Safety Laboratory Assessments

- See [Appendix 11](#) for the list of clinical laboratory tests to be performed and the SoA for the timing and frequency.
- For the three visits requiring fasted labs (Baseline, Day 113, and Day 127), a subject should refrain from eating or drinking (except for water) for a period of at least 8 hours prior to the lab draw.
- The Investigator must review the laboratory report, document this review, and record any clinically relevant changes occurring during the study in the AE section of the CRF. The laboratory reports must be filed with the source documents. Clinically significant abnormal laboratory findings are those that are not associated with the underlying disease, unless judged by the Investigator to be more severe than expected for the subject's condition.
- All laboratory tests with values considered clinically significantly abnormal during participation in the study or within 30 days after the last dose of study treatment should be repeated until the values return to normal or baseline or are no longer considered clinically significant by the Investigator or Medical Monitor.
 - If such values do not return to normal/baseline within a period of time judged reasonable by the Investigator, the etiology should be identified and the Medical Monitor and Sponsor notified.
 - All protocol-required laboratory assessments, as defined in [Appendix 11](#), must be conducted in accordance with the laboratory manual and the SoA.
 - If laboratory values from non-protocol specified laboratory assessments performed at the institution's local laboratory require a change in subject management or are considered clinically significant by the Investigator (e.g., SAE or AE or dose modification), then the results must be recorded in the CRF.

8.3 Adverse Events

The definitions of an AE or SAE can be found in [Appendix 12](#).

AEs will be reported by the subject (or, when appropriate, by a caregiver, surrogate, or the participant's legally authorized representative).

The Investigator and any designees are responsible for detecting, documenting, and recording events that meet the definition of an AE or SAE and remain responsible for following up AEs that are serious, considered related to the study treatment or study procedures, or that caused the subject to discontinue the study treatment or the study (see [Section 7.0](#)).

8.3.1 Time Period and Frequency for Collecting AE and SAE Information

Adverse events and SAEs will be collected from the signing of the ICF until Follow-up /Visit 10 or 28 days after the last dose of study treatment if subject is terminated early.

All SAEs will be recorded and reported to the Sponsor or designee within 24 hours of the Investigator's awareness of the event, as indicated in [Appendix 12](#). The Investigator will submit any updated SAE data to the Sponsor within 24 hours of receipt of the information.

Investigators are not obligated to actively seek AE or SAE after conclusion of the study participation. However, if the Investigator learns of any SAE, including a death, at any time after a subject has been discharged from the study, and he/she considers the event to be reasonably related to the study treatment or study participation, the Investigator must promptly notify the Sponsor.

The method of recording, evaluating, and assessing causality of AE and SAE and the procedures for completing and transmitting SAE reports are provided in [Appendix 12](#).

8.3.2 Method of Detecting AEs and SAEs

Care will be taken not to introduce bias when detecting AEs and/or SAEs. Open-ended and non-leading verbal questioning of the subject is the preferred method to inquire about AE occurrences.

8.3.3 Follow-up of AEs and SAEs

After the initial AE/SAE report, the Investigator is required to proactively follow each subject at subsequent visits/contacts. All SAEs will be followed until resolution, stabilization, the event is otherwise explained, or the subject is lost to follow-up (as defined in [Section 7.3](#)). Further information on follow-up procedures is given in [Appendix 12](#).

8.3.4 Regulatory Reporting Requirements for SAEs

- Prompt notification by the Investigator to the Sponsor of an SAE is essential so that legal obligations and ethical responsibilities towards the safety of subjects and the safety of a study treatment under clinical investigation are met.
- The Sponsor has a legal responsibility to notify both the local regulatory authority and other regulatory agencies about the safety of a study treatment under clinical investigation. The Sponsor will comply with country-specific regulatory requirements relating to safety reporting to the regulatory authority, IRBs/REBs/IECs, and Investigators.
- Investigator safety reports must be prepared for suspected unexpected serious adverse reactions (SUSAR) according to local regulatory requirements and Sponsor policy and forwarded to Investigators as necessary.
- An Investigator who receives an Investigator safety report describing an SAE or other specific safety information (e.g., summary or listing of SAEs) from the Sponsor will review

and then file it along with the Investigator's Brochure and will notify the IRB/REB/IEC, if appropriate according to local requirements.

8.3.5 Adverse Events of Clinical Interest

Events of clinical interest, whether serious or not, in the study include:

- malignancy
- major adverse cardiac events (MACE)
- tuberculosis (TB)
- inflammatory bowel disease (IBD)
- depression and suicidal ideation and behavior
- serious or opportunistic infection
- hypersensitivity reactions

RPT193 has not been associated with any of these events of clinical interest based on preclinical toxicology studies as well as clinical Phase 1 data from RPT193-01. These events of clinical interest will be evaluated on an ongoing basis. A separate analysis of these adverse events will also be performed at the end of the study.

8.3.6 Pregnancy

- Details of all pregnancies in female subjects and, if indicated, female partners of male subjects, will be collected after the start of study treatment and until 30 days after the last administration of study treatment.
- If a pregnancy is reported, the Investigator should inform the Sponsor within 24 hours of learning of the pregnancy and should follow the procedures outlined in [Appendix 12](#).
- If the outcome of the pregnancy meets the criteria for immediate classification as an SAE (i.e., spontaneous abortion, stillbirth, neonatal death, or congenital anomaly [including that in an aborted fetus, stillbirth, or neonatal death]), the Investigator will report according to the SAE reporting procedures described in [Appendix 12](#).

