 12. For male subject involved in any sexual intercourse that could lead to pregnancy, subject must agree to use one of the highly effective contraceptive methods listed in Inclusion Criterion #10, from Baseline (Day 1) until at least 90 days after the last study drug administration. If the female partner of a male subject uses any of the hormonal contraceptive methods listed above, this contraceptive method should be used by the female partner from at least 4 weeks before Baseline (Day 1) until at least 90 days after the last study drug administration.
 13. Male agrees not to donate sperm during the study and for 90 days after the last study drug administration.
 14. Subject has negative COVID-19 results at Screening.
 15. Subject is willing to comply with discontinuation of prohibited treatments for AD as described in [Table 3](#) for the duration of the study, as directed by the Investigator.
 16. Subject is willing to participate and is capable of giving informed consent.
Note: Consent must be obtained prior to any study-related procedures.
 17. Subject must be able and willing to comply with all study procedures and must be available for the duration of the study.

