Appendix 13 **Contraceptive Guidance and Collection of Pregnancy Information**

Definitions:

Woman of Childbearing Potential (WOCBP)

A woman is considered fertile following menarche and until becoming postmenopausal unless permanently sterile (see below).

Women in the following categories are not considered WOCBP

1. Premenarchal
2. Premenopausal female with one of the following:
 - a) Documented hysterectomy.
 - b) Documented bilateral salpingectomy.
 - c) Documented bilateral oophorectomy.
Note: Documentation can come from the study center personnel's: review of the subject's medical records, medical examination, or medical history interview.
3. Postmenopausal female:
 - a) A postmenopausal state is defined as no menses for 12 months without an alternative medical cause. A high follicle-stimulating hormone (FSH) level in the postmenopausal range may be used to confirm a postmenopausal state in women not using hormonal contraception or hormonal replacement therapy (HRT). However, in the absence of 12 months of amenorrhea, a single FSH measurement is insufficient.
 - b) Females on HRT and whose menopausal status is in doubt will be required to use 1 of the non-estrogen hormonal highly effective contraception methods if they wish to continue their HRT during the study. Otherwise, they must discontinue HRT to allow confirmation of postmenopausal status before study enrollment.

Contraception Guidance

Male subjects

- Male subjects with female partners of childbearing potential are eligible to participate if they agree to ONE of the following [during the protocol-defined time frame in [Section 5.1](#)]:
 - Are abstinent from penile-vaginal intercourse as their usual and preferred lifestyle (abstinent on a long-term and persistent basis) and agree to remain abstinent.
 - Agree to use a male condom plus partner use of a contraceptive method with a failure rate of <1% per year as described in the table below when having penile-vaginal intercourse with a woman of childbearing potential who is not currently pregnant.
- In addition, male subjects must refrain from donating sperm for the duration of the study and for 90 days after the last dose of study treatment.

- Male subjects with a pregnant or breastfeeding partner must agree to remain abstinent from penile-vaginal intercourse or use a male condom during each episode of penile penetration for the duration of the study and 90 days after the last dose of study treatment.

Female subjects

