
NOTES: ^a Use should be consistent with local regulations regarding the use of contraceptive methods for subjects participating in clinical studies. ^b Female study participants who are women of childbearing potential using one of the highly effective, hormonal contraceptives described above (either birth control pills or implantable devices) will be required to also employ a barrier method of contraception (e.g., condom use by a male partner, diaphragm, or cervical cap) for a minimum of 30 days following the last dose of study drug. Male study participants with partners who are women of childbearing potential using one of the highly effective, hormonal contraceptives described above (either birth control pills or implantable devices) will be required to also employ a barrier method of contraception (e.g., condom use by a male partner, diaphragm, or cervical cap) for a minimum of 90 days following the last dose of study drug.

Pregnancy Testing:

- WOCBP should only be included after a negative highly sensitive serum pregnancy test.
- Additional pregnancy testing should be performed at the times specified in the SoA during the study period after the last dose of study treatment and as required locally.
- Pregnancy testing will be performed whenever a menstrual cycle is missed or when pregnancy is otherwise suspected.

Collection of Pregnancy Information***Male subjects with partners who become pregnant***

- The Investigator will attempt to collect pregnancy information on any male subject's female partner who becomes pregnant while the male subject is in this study. This applies only to male subjects who receive RPT193.
- After obtaining the necessary signed informed consent from the pregnant female partner directly, the Investigator will record pregnancy information on the appropriate form and submit it to the Sponsor or designee within 24 hours of learning of the partner's pregnancy. The female partner will also be followed to determine the outcome of the pregnancy. Information on the status of the mother and child will be forwarded to the Sponsor. Generally, the follow-up will be no longer than 6 to 8 weeks following the estimated delivery date. Any termination of the pregnancy will be reported regardless of fetal status (presence or absence of anomalies) or indication for the procedure.

Female Subjects who become pregnant

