- The Investigator will collect pregnancy information on any female subject who becomes pregnant while participating in this study. Information will be recorded on the appropriate form and submitted to the Sponsor or designee within 24 hours of learning of a subject's pregnancy. The subject will be followed to determine the outcome of the pregnancy. The Investigator will collect follow-up information on the subject and the neonate and the information will be forwarded to the Sponsor or designee. Generally, follow-up will not be required for longer than 6 to 8 weeks beyond the estimated delivery date. Any termination of pregnancy will be reported, regardless of fetal status (presence or absence of anomalies) or indication for the procedure.
- While pregnancy itself is not considered to be an AE or SAE, any pregnancy complication will be reported as an AE or SAE. If the outcome of the pregnancy meets the criteria for immediate classification as an SAE (i.e., spontaneous abortion, stillbirth, neonatal death, or congenital anomaly [including that in an aborted fetus, stillbirth, or neonatal death]), the investigator will report according to the SAE reporting procedures described in [Appendix 12](#).

- Any post-study pregnancy related SAE considered reasonably related to the study treatment by the Investigator will be reported to the Sponsor or designee as described in [Section 8.3.4](#). While the Investigator is not obligated to actively seek this information in former subjects, he or she may learn of an SAE through spontaneous reporting.
- Any female subject who becomes pregnant while participating in the study will discontinue study treatment.

Reporting Pregnancy Information

Email transmission of the paper Pregnancy Report Form is the preferred method to transmit safety event information to [REDACTED] with facsimile as a back-up method, if necessary.

Safety events should be reported to [REDACTED] at:

Email: [REDACTED]

Fax: [REDACTED]

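### Partner-pregnancy collection has two different end points, both short of the 90-day male precaution period for full-course completers and early leavers, and an arm limit that blinded sites cannot apply

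*Protocol*

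**What the plan says.** Protocol 8.3.6 sets one collection window for both sexes. It names female subjects first and then adds: "if indicated, female partners of male subjects, will be collected after the start of study treatment and until 30 days after the last administration". The condition attached to partners is not defined. A reported pregnancy goes to the Sponsor within 24 hours, and this sentence has no limit by treatment arm.

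Appendix 13 sets a different end point. For males, the investigator attempts to collect information on any female partner "who becomes pregnant while the male subject is in this study". It then adds: "This applies only to male subjects who receive RPT193". After obtaining the partner's consent, the investigator must complete the form and "submit it to the Sponsor or designee within 24 hours of learning" of the pregnancy. For females, it covers "any female subject who becomes pregnant while participating in this study".

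The male precaution period is longer than either window usually is. Inclusion criterion 12 requires contraception "from Baseline (Day 1) until at least 90 days after the last study drug administration". Appendix 13 repeats the 90 days for sperm donation and, in note b, for barrier use with partners on hormonal methods. The matching female contraception period is 30 days (criterion 10).

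Protocol 6.3 withholds treatment assignment from the investigator, study staff, CRO and Sponsor study team until after the study. It reserves code breaks for safety emergencies.

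**The concern.** Two parts of one protocol tell a site to stop collecting the same information at different times, and neither refers to the other. A site working from 8.3.6 alone stops at 30 days. A site working from Appendix 13 alone stops when the subject leaves.

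The protocol separates the sexes for precautions (30 days for females, 90 for males), but 8.3.6 applies the 30-day figure to both. For many males, collection therefore ends inside the period in which the sponsor itself asks them to avoid conception.

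The RPT193-only sentence is addressed to someone who does not know the arm. Read literally, it could lead a site to hold back a report or to ask for a code break. Under 6.3 an unblinded subject is normally discontinued. At stake is how complete the pregnancy data are for a drug in early development.

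**Working it through.** **Inputs**
- Last planned dose: Day 112 (Protocol 1.3, footnote k).
- Last follow-up visit: Day 169, window ±3 days, so Day 166 to 172 (Protocol 1.3 and 4.1).
- 8.3.6 window: 30 days after last dose.
- Appendix 13 window: end of the male subject's participation.
- Male precaution period: 90 days after last dose (criterion 12; Appendix 13, sperm-donation bullet and note b).

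**Plan's own figure.** Protocol 6.0 gives a 56-day follow-up: 169 − 113 = 56, reproduced. Dosing ends the day before Day 113, so time off drug at the last visit is 169 − 112 = 57 days (166 − 112 = 54 to 172 − 112 = 60).

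**End points for a full-course completer**
- 8.3.6: 112 + 30 = Day 142.
- Appendix 13: Day 169 (166 to 172).
- Male precautions: 112 + 90 = Day 202.
- Difference between the two collection windows: 169 − 142 = 27 days (24 to 30).

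**Shortfall with both sections applied.** Let L be the day of last dose and E the day participation ends. Collection lasts for the longer of 30 and E − L days, so

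uncovered days = max(0, 90 − max(30, E − L)).

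- Full-course completer: 90 − 57 = 33 days (90 − 60 = 30 to 90 − 54 = 36). As a share, 33/90 = 37% (30/90 = 33% to 36/90 = 40%).
- Male who leaves within 30 days of last dose, for example at the ET/Discon visit: 90 − 30 = 60 days. Here Appendix 13 alone would give less than 30 days, so the order of the two windows reverses.
- Male who leaves between 30 and 90 days after last dose: 90 − (E − L), between 60 and 0 days.
- Male who stops drug early but stays to Day 169: 0 days when L ≤ 169 − 90 = Day 79 (Day 76 to 82 with the visit window).

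**Female completers.** 8.3.6 ends at Day 142 and Appendix 13 at Day 169. With both applied, collection runs to Day 169, beyond the 30-day female contraception period. The sections disagree, but no coverage is lost.

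**The arm limit.** The instruction is to the investigator (Appendix 13), the deadline is 24 hours (Appendix 13 and 8.3.6), and the investigator is blinded (6.3). A partner pregnancy is not a stated ground for a code break. The only way for a blinded site to comply is to report every partner pregnancy and leave the limit to be applied after unblinding. The text does not say this.

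**Does another section close the gap?** Protocol 8.3.1 covers SAEs after discharge, but only those the investigator learns of and considers reasonably related. Appendix 13 has a post-study clause, "While the Investigator is not obligated to actively seek this information in former subjects", but it sits under female subjects and concerns related SAEs. Appendix 13 also states that pregnancy is not in itself an AE or SAE. Neither route collects a partner pregnancy as such.

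**The case against.** The best reply is that the 90-day period is a precaution and not a reporting rule. Nothing in the documents ties pregnancy collection to it, and the toxicology section is partly redacted, so the sponsor's reason for 90 days cannot be judged. What can be seen points to low residual risk: a half-life of about 24 hours (2.2.2.4) and no genotoxicity (2.2.2.3). This stands as a limit on severity. It does not explain why two sections give different end points, nor why the female figure is used for males when the sponsor set 90 days for them.

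Second, a site can meet every instruction by reporting all partner pregnancies under 8.3.6, which has no arm limit. Appendix 2 (Table 6) places the randomization code with Sponsor/CRO, so the limit could be applied later. This is correct, and it reduces the blinding issue to one misdirected sentence.

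Third, serious outcomes keep a passive route through 8.3.1 and the third bullet of 8.3.6. That is also true, but it is narrower than collecting pregnancies.

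A reader might infer more than the text supports:
- That no male is ever covered to 90 days. This fails for those who stop by about Day 79 and remain to Day 169. The primary estimand expects data after treatment discontinuation, so such subjects can exist.
- That female pregnancies are missed. For completers they are not, when both sections are applied. The schedule in SAP Appendix I includes a pregnancy test at Day 169.
- That every 90-day clause in Appendix 13 is about preventing conception. The clause "for the duration of the study and 90 days after the last dose of study treatment" concerns males whose partner is already pregnant or breastfeeding, so it is not relied on here.

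**Conclusion.** The point holds in limited form. The two sections give different end points for partner-pregnancy collection, 27 days apart for a full-course completer (24 to 30). With both applied, about 33 of the 90 days after last dose (30 to 36) have no active collection for completers, and up to 60 days for males who leave soon after stopping drug. The RPT193-only limit cannot be applied by the blinded investigator to whom it is addressed.

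The figures assume last dose on Day 112 for completers, the ±3-day visit window, and the sponsor's own 90 days as the yardstick. They are calendar days, not risk. The number of pregnancies affected cannot be estimated from the documents. A reader might infer that fetal harm is likely or that the trial's conclusions are at risk. The documents support neither: this is about completeness of safety reporting, and efficacy, power and type I error are untouched. Severity is low.

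**What to change.** - **Appendix 13:** delete "This applies only to male subjects who receive RPT193".
- **8.3.6 (replacing the undefined condition on partners) and Appendix 13:** state that partner pregnancies are collected for all male subjects, from first dose until the later of end of participation or 90 days after last dose.
- **Last or ET/Discon visit:** instruct each male subject to report any partner pregnancy in that period. An instruction alone still relies on the subject; an optional later contact would make collection active.
- **Editorial:** give female subjects one window in both sections (the later of end of participation or 30 days after last dose), and point the procedures reference in 8.3.6 to Appendix 13, where the pregnancy procedures are, and not Appendix 12.

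**Cost.** One instruction per male subject. A few placebo partner pregnancies would be followed, with the partner consent Appendix 13 already requires. For early terminators the period runs past the 28-day AE limit in 8.3.1, so the text should say that this is intended. Appendix 2 requires an amendment with ethics approval, regulatory approval where applicable, and re-consent if the consent form is revised.
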